3.2.2 Event-Free Survival

Event-free survival will be estimated at 12 months after HCT. Grade III-IV acute GVHD and chronic GVHD requiring systemic immune suppression will be considered in this estimate.^{61,62} An event is defined as death due to any cause, primary or secondary graft failure/rejection, or 2nd HCT whichever occurs first.

Primary Graft Failure/Rejection: defined as never achieving ANC $\geq 500/\mu\text{L}$ or never achieving $\geq 5\%$ donor myeloid chimerism assessed by peripheral blood chimerism assays by day +42 post-HCT. Second infusion of hematopoietic cells is also considered indicative of primary graft failure by day +42 post-HCT.

Secondary Graft Failure/Rejection: defined as $< 5\%$ donor myeloid chimerism in peripheral blood beyond day +42 post-HCT in patients with prior documentation of hematopoietic recovery with $\geq 5\%$ donor cells by day +42 post-HCT. Second infusion of hematopoietic cells is also considered indicative of secondary graft failure.

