3.2.3 Hematologic Recovery

Hematologic recovery will be assessed according to neutrophil and platelet counts recovery after transplant. Neutrophil recovery will be estimated at day 28 and platelet recovery at day 100 after HCT.

Neutrophil recovery is defined as achieving an absolute neutrophil count (ANC) $\geq 500/\text{mm}^3$ for 3 consecutive measurements on 3 different days. The first of the three days will be designated the day of neutrophil recovery. The competing event is death without neutrophil recovery.

Platelet recovery is defined as the first day of a minimum of 3 days that the patient has a sustained platelet count $\geq 20,000/\text{mm}^3$ with no platelet transfusions in the preceding 7 days. The first day of sustained platelet count above these thresholds will be designated the day of platelet engraftment.

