Graft failure is expected to be no higher than 10% by 100 days. Graft failure within 100 days will be monitored using a sequential probability ratio test (SPRT) for binary data that compares a rate of 10% under the null hypothesis to a rate of 30% under the alternative hypothesis. This sequential testing procedure preserves the type I error rate at a prespecified level across all of the monthly examinations. The binary SPRT can be represented graphically by plotting the number of evaluable patients against the cumulative number of events. The continuation region of the SPRT is defined by two parallel lines. Only the upper boundary will be used for monitoring in order to protect against excessive Day 100 graft failure rates. If the cumulative number of graft failures falls above the upper boundary the SPRT rejects the null hypothesis and concludes that more graft failures occurred than should be expected in the observed number of evaluable patients. Otherwise, the SPRT continues until enrollment reaches the target sample size of 40 patients. The binary SPRT can be displayed in a tabular form, as shown in **Table 17**. This table gives the rejection boundaries for the number of Day 100 graft failure events corresponding to the number of evaluable patients. At least three graft failures must be observed in order to trigger review.

This procedure considers only graft failures occurring by Day 100. A binary SPRT contrasting 10% versus 30% Day 100 graft failure rates results in decision boundaries with a common slope of 0.1862 and an upper intercept of 1.7984 with nominal type I and II error rates of 7.5% and 15%, respectively. Because the SPRT employed here is truncated at a sample size of 40 and only uses the upper decision boundary, the actual type I and II errors will vary from these nominal levels.

Table 17: Sequential Monitoring Plan based on Binary SPRT for Graft failure by day 100

Number of Evaluable Patients	Rejection Boundary for # of graft failures by day 100
3-6	3
7-11	4
12-17	5
18-22	6
23-27	7
28-33	8
34-38	9
39-40	10

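### Primary graft failure in Section 3.2.2 carries no condition that the patient be alive or assessable, so deaths before engraftment can be counted as graft failures

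*Protocol*

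**What the plan says.** Section 3.2.2 gives the only operative definition of primary graft failure: "Primary Graft Failure/Rejection: defined as never achieving ANC" of at least 500/µL, or never reaching at least 5% "donor myeloid chimerism assessed by peripheral blood chimerism assays by day +42 post-HCT". A second infusion of cells by day +42 also qualifies. Survival to day +42 is not mentioned.

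The same section defines EFS so that death counts in its own right: "An event is defined as death due to any cause, primary or secondary graft failure/rejection, or 2nd HCT whichever occurs first".

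For neutrophil recovery, Section 3.2.3 does deal with early death: "The competing event is death without neutrophil recovery". Sections 5.7.3, 5.7.5, 5.7.6 and 5.7.8 likewise make death a competing event for neutrophil and platelet recovery, acute and chronic GVHD, and CMV/EBV reactivation. No such statement is made for graft failure, although primary graft failure at day 42 is part of secondary objective 5.

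The graft-failure monitoring rule in Section 5.3 "compares a rate of 10% under the null hypothesis to a rate of 30% under the alternative hypothesis" and adds: "This procedure considers only graft failures occurring by Day 100". It plots events against evaluable patients. Section 5.3 says what evaluable means for the mortality rule (died, or followed for 100 days) but not for this one.

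**The concern.** A patient who dies on day 12 without count recovery has, by the wording of Section 3.2.2, never reached the threshold by day +42. The label fits although the graft had no time to succeed or fail.

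The chimerism limb lengthens the exposed period. Table 13 and Section 4.3.4 schedule the first post-transplant assay at day +28, and a day +42 assay only if day +28 was missed. A patient who recovers neutrophils on day 18 and dies on day 24 would usually have no assay, and so has never shown 5% donor cells by assay.

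Two results are at stake. The estimate for secondary objective 5 would mix early deaths with failure to engraft. If the monitoring rule uses the same definition, its false-trigger rate would exceed the value in Table 18, and the same deaths would feed both safety rules, which are meant to watch different hazards.

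**Working it through.** **Step 1. Reproduce the plan's rule.** Inputs from Section 5.3: p0 = 0.10, p1 = 0.30, nominal errors 0.075 and 0.15, at least three events, and a test "truncated at a sample size of 40 and only uses the upper decision boundary".

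- k = ln[p1(1−p0)/(p0(1−p1))] = ln(0.27/0.07) = 1.3499
- slope = ln(0.9/0.7)/k = 0.2513/1.3499 = 0.1862
- upper intercept = ln(0.85/0.075)/k = 2.4277/1.3499 = 1.7984

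These match the stated "a common slope of 0.1862 and an upper intercept of 1.7984 with nominal type I and II error rates of 7.5% and 15%, respectively". The boundary max(3, ceiling(1.7984 + 0.1862n)) reproduces every row of Table 17. An exact binomial recursion with one look per evaluable patient gives rejection probabilities of 0.052, 0.485, 0.741 and 0.902 at true rates of 10%, 20%, 25% and 30%. Table 18 states 0.052, 0.484, 0.736 and 0.898. The rule itself is sound.

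**Step 2. Deaths in the exposed window.** The protocol gives no pre-engraftment death rate, so this is an assumption. With a constant hazard (the exponential form Section 5.3 uses for mortality), q = 1 − (1−m)^(d/100), where:

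- m is day-100 mortality. The low value, 3%, borrows the day-200 transplant-related mortality of the 80-patient series in Section 1.3.4. The middle value is the registry's 100 − 92.4 = 7.6% (Section 1.3.2). The high value, 15%, is the ceiling expected in Section 5.3.
- d is 22 days (median neutrophil recovery in the pilot, Section 1.2) or 28 days (first scheduled chimerism assay).

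**Step 3. Counted rate and trigger probability.** If every such death is counted and is independent of graft failure, the counted rate is q + (1−q)g, where g is the true graft-failure rate. For example, m = 15% and d = 28 give q = 1 − 0.85^0.28 = 0.0445, and g = 10% becomes 0.0445 + 0.9555 × 0.10 = 0.140. The counted rate goes through the Step 1 recursion.

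| m | d | q | Counted rate, g = 10% | P(trigger), g = 10% | P(trigger), g = 3.8% |
|---|---|---|---|---|---|
| none counted | – | 0 | 10.0% | 0.052 | 0.002 |
| 3% | 22 | 0.7% | 10.6% | 0.065 | 0.003 |
| 3% | 28 | 0.8% | 10.8% | 0.069 | 0.003 |
| 7.6% | 22 | 1.7% | 11.6% | 0.089 | 0.006 |
| 7.6% | 28 | 2.2% | 12.0% | 0.101 | 0.008 |
| 15% | 22 | 3.5% | 13.2% | 0.140 | 0.015 |
| 15% | 28 | 4.4% | 14.0% | 0.173 | 0.024 |

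The 3.8% column uses the registry's day-100 graft failure with ATG (Section 1.3.2). The net rise in the counted rate is q(1−g), slightly less than q: 0.6 to 4.0 points at g = 10%.

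**Step 4. EFS and GEFS.** Death is already an event in both, so relabelling an early death adds none.

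**The case against.** A reader might infer that Sections 3.2.2 and 3.2.3 contradict each other. They do not: one defines graft failure, the other names the competing event for neutrophil recovery, and a rule for one endpoint does not settle the other.

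A reader might also infer that the monitoring rule is known to count these deaths. The text does not go that far. Section 5.3 does not cite Section 3.2.2, and evaluable could be read to exclude early deaths. The protocol neither includes nor excludes them, so the effect on the trigger is conditional.

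The consequences are also modest. In the treosulfan series of Section 1.3.4, day-100 transplant-related mortality was 0% in the first 31 patients and no bone marrow failure patient rejected. The largest trigger probabilities need graft failure at the 10% null and mortality at its 15% ceiling together. A crossing prompts DSMB review, where an early death would be recognised.

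Two further arguments carry less weight. Endpoint Review Committee adjudication (Section 5.5.1) is tied to the primary analysis, whereas the rule is checked monthly and at each event, so the classification is needed during accrual. Competing-risk estimation may well be left to an SAP, but the definition is stated in the protocol, and as worded it captures these deaths.

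One objection bears on the remedy. Pilot neutrophil recovery was complete by day 26, so a patient who dies aplastic on day 40 may truly have failed to engraft. Rejection may go undocumented, because the day +28 assay is done only if ANC has recovered. Excluding all such deaths would lose that information, and the fix allows for this.

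**Conclusion.** The definition should be corrected. Applied as written, it labels death before engraftment or before the first assay as primary graft failure and would raise the estimate for secondary objective 5. Whether the Section 5.3 rule is affected depends on a term the protocol leaves undefined.

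If these deaths are counted, the trigger probability at a true 10% is about 1.2 times (0.065/0.052) to 3.3 times (0.173/0.052) the stated value, but it remains small at the registry's graft-failure rate. These figures rest on a constant hazard, a borrowed range for day-100 mortality, independence of death and graft failure, and counting every death by day 22 to 28.

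The primary endpoint, EFS, the sample size, the Table 17 boundaries and the Table 18 figures are not in question.

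**What to change.** In Section 3.2.2, state for both the ANC and the chimerism limb that death before day +42 without documented rejection or second infusion is a competing event for graft failure, not a graft failure. Estimate graft failure by cumulative incidence, as for the other endpoints. In Section 5.3, define an evaluable patient for the graft-failure rule consistently with this.

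List deaths before day +42 without engraftment separately for the DSMB, so that a late aplastic death is not lost when it no longer counts automatically. All these deaths are still captured by the mortality rule.

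The cost is a few sentences and one listing. No new data, boundary or sample-size change is needed.

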3.2.3 Hematologic Recovery

Hematologic recovery will be assessed according to neutrophil and platelet counts recovery after transplant. Neutrophil recovery will be estimated at day 28 and platelet recovery at day 100 after HCT.

Neutrophil recovery is defined as achieving an absolute neutrophil count (ANC) $\geq 500/\text{mm}^3$ for 3 consecutive measurements on 3 different days. The first of the three days will be designated the day of neutrophil recovery. The competing event is death without neutrophil recovery.

Platelet recovery is defined as the first day of a minimum of 3 days that the patient has a sustained platelet count $\geq 20,000/\text{mm}^3$ with no platelet transfusions in the preceding 7 days. The first day of sustained platelet count above these thresholds will be designated the day of platelet engraftment.

3.2.4 Donor Chimerism (CD3 and Myeloid)

Donor cell engraftment will be assessed with donor/recipient chimerism studies at day 28, 100, 180, and 1 year after HCT. Chimerism will be evaluated in fractionated blood for CD3 T-cell and myeloid (CD33 or CD15). Peripheral blood myeloid donor chimerism will be used to define the donor/recipient chimerism status.

Full donor chimerism is defined as $\geq 95\%$ donor cells in the myeloid fraction.

Mixed donor chimerism/engraftment is defined as the presence of 5-94.99% donor cells in the myeloid fraction.

Graft rejection is defined as $< 5\%$ donor cells in the myeloid fraction.

3.2.5 Acute GVHD

The cumulative incidences of acute grade II-IV and III-IV GVHD at day 100 and day 180 after HCT will be determined. Acute GVHD by day 100 and day 180 will be graded according to the BMT CTN Technical guidelines on Acute GVHD and based on the Mount Sinai Acute GVHD International Consortium (MAGIC) criteria (**Appendix F**).⁶¹ The time of onset of acute grades II-IV and III-IVGVHD will be recorded, as well as the maximum grade achieved at day 100 and day 180.

3.2.6 Chronic GVHD

The cumulative incidence of chronic GVHD (using NIH consensus criteria) requiring systemic immune suppression at 1 year after HCT will be determined. Data will be collected directly from providers and chart review as defined by the NIH Consensus Conference Criteria (**Appendix G**).⁶² Eight organs will be scored on a 0-3 scale to reflect the degree of chronic GVHD involvement. Liver and pulmonary function test results and use of systemic therapy for treatment of chronic GVHD will also be recorded. These data will allow calculation of the NIH global severity scores of mild, moderate, and severe chronic GVHD, which has been associated with transplant related mortality and overall survival. Assessment of chronic GVHD will occur up to 1 year after transplant.

3.2.7 Grade 3-5 Toxicities

Grade 3-5 toxicities by day 30 and day 100 after HCT, according to the BMT CTN MOP, will be collected.

3.2.8 Systemic Infections

All microbiologically documented infections or significant infections requiring antibiotic/antifungal therapy occurring up to 6 months after HCT will be reported by disease type (bacterial, fungal, viral, etc.), date of onset, and severity. For definitions see the BMT CTN Technical guidelines located on the BMT CTN Website.

3.2.9 EBV Reactivation

The incidence of EBV reactivation requiring therapy in the first 180 days after HCT, and of EBV-associated lymphoproliferative disorder in the first 180 days after HCT will be evaluated.

3.2.10 CMV Reactivation

The incidence of CMV reactivation requiring therapy in the first 180 days after HCT will be evaluated.

3.3 Exploratory Endpoints

3.3.1 Pharmacokinetic Studies

Treosulfan pharmacokinetic studies will be performed from peripheral blood samples if consent is obtained from subjects/guardians. This is an optional research study (**Appendix E**).

3.3.2 Biological Studies

Biological studies will be performed if consent is obtained from subjects/guardians. Prior to the initiation of the preparative regimen, blood and marrow samples (if obtained clinically a research specimen will be collected; cells, DNA, serum) will be banked. If samples have been donated and subject does not continue to transplant, samples will be stored for future research. Fibroblast cultures will be established from marrow aspirates as a source of germline DNA. Studies will include:

1. Assess clonal hematopoiesis before and after HCT in pediatric BMFD.

Rationale: Clonal hematopoiesis with acquisition of mutations associated with myeloid malignancies are common in children with BMFD. The host marrow niche may contribute to clonal hematopoiesis but the effect of HCT on clonal hematopoiesis has not been studied in patients.

Methods:

- Deep error-corrected targeted sequencing of genes mutated in myeloid malignancies and bone marrow failure.
- Assess somatic mutations (type, number, mutational spectrum) and variant allele frequencies before and after HCT.

2. Measure cytokine levels before and after HCT.

Rationale: Inflammation contributes to the pathogenesis of bone marrow failure and may also contribute to clonal evolution.

Methods:

- Marrow plasma cytokine levels, particularly inflammatory cytokines, will be measured before and after HCT.

These biological studies will be correlated with clinical outcomes for study subjects (**Appendix E**). This is an optional research study.

3.3.3 Mutational Testing

Mutational testing will be performed for patients who lack a known genetic mutation responsible for their bone marrow failure phenotype, if consent is obtained from subjects/guardians. Prior to the initiation of the preparative regimen, peripheral blood will be obtained for whole exome/genome sequencing (**Appendix E**). This is an optional research study.

3.3.4 Health Related Quality of Life

Health-related quality of life using the PROMIS instruments will be performed at baseline, day +180 and day +365 post-HCT, if consent is obtained by subjects/guardians. Patients aged 8-17 at the time of assessment will complete pediatric instruments. Proxy reports (e.g., parents, guardians) will be collected for patients aged 5 to 8. The PROMIS instruments are available in Spanish and English. Patients who do not speak Spanish or English will not complete the health-related quality of life surveys (**Appendix H**). This is an optional research study.

CHAPTER 4

4 PATIENT ENROLLMENT AND STUDY EVALUATIONS

4.1 Disease and Donor Screening Procedures

Patients are identified and recruited by their physician, usually a hematologist and are referred to an HCT physician for further consultation. This consultation includes a detailed review of the trial design, the anticipated benefits and complications, and compliance including availability at 1-year post-HCT for trial assessments.

The order of events for patient enrollment is as follows:

1. Interested patients will sign an NMDP IRB-approved study consent form which will include consent for screening assessments to determine if the patient's underlying disease is eligible for this study.
2. The patient will be entered into Advantage eClinical Segment 0.
 - a. If required per inclusion criteria, the patient will be reviewed by the BMT CTN 1904 protocol Eligibility Review Committee (ERC) for determination of disease eligibility for this clinical trial (**See Appendix B**).
 - b. If the potential patient is deemed eligible by disease by the BMT CTN 1904 protocol eligibility review committee, the potential patient will then proceed forward with local assessment of eligibility criteria.
3. If ERC review is not required per inclusion criteria, the potential patient will then proceed forward with local assessment of eligibility criteria.
4. The patient will be enrolled into Segment A in Advantage eClinical, a web-based data collection system.

4.2 Enrollment Procedures

Patients will be registered using the BMT CTN Electronic Data Capture System (Advantage eClinical). The following procedures should be followed:

1. An authorized user at the transplant center completes the Demographics Form and Segment 0 Enrollment Form in Advantage eClinical, at which point a study number will be generated.
 - a. Patients requiring protocol ERC review per inclusion criteria:
 - i. Enrollment into Segment 0 must be completed prior to submission to the protocol ERC. Once enrolled into Segment 0, the patient's medical records for the ERC can be updated to the system.
 - ii. Following ERC review, if the patient is found to be eligible for the study, the authorized user will complete any required Segment 0 forms and then be able to enroll the patient on Segment A using the Segment A Enrollment Form.
 - b. If not undergoing an ERC review, the authorized user will complete any required Segment 0 forms in Advantage eClinical and then if the patient is still eligible for the study, the authorized user will be able to enroll the patient on Segment A using the Segment A Enrollment Form.

2. The patient is not officially enrolled on study and may not begin study treatment until they are enrolled on Segment A. If the patient is found to be not eligible for the study, the site will indicate this in the data system.
3. Patients should not be enrolled into Segment A more than 14 days prior to the planned initiation of conditioning. If initiation of conditioning has not started within 14 days of enrollment, the Protocol Coordinator and Protocol Chairs and Officer must be notified.
4. A visit schedule based on transplant date is displayed in the Forms Grid.

4.3 Study Monitoring

4.3.1 Follow-Up Schedule

The follow-up schedule for study visits is outlined in **Table 12**. A detailed description of each of the forms and the procedures required for forms completion and submission can be found in the Data Management Handbook and User’s Guide.

Table 12: Follow-Up Schedule	
Study Visit	Target Day Post-HCT
Day of Transplant	Day 0*
Day 2	Day 2
1 week	7 ± 3 days
2 weeks	14 ± 3 days
3 weeks	21 ± 3 days
4 weeks	28 ± 3 days
5 weeks	35 ± 3 days
6 weeks	42 ± 3 days
7 weeks	49 ± 3 days
8 weeks	56 ± 3 days
9 weeks	63 ± 3 days
10 weeks	70 ± 3 days
11 weeks	77 ± 3 days
12 weeks	84 ± 3 days
13 weeks	91 ± 7 days
100 days	100 ± 7 days
6 months	180 ± 28 days
12 months	365 ± 28 days
*Additional rest days may be added given delays that may occur with stem cell collection, transportation, processing. The actual day the stem cell infusion finishes will remain “Day 0”.	

4.3.2 Patient Assessments

Table 13 summarized patient clinical assessments over the course of the study. See **Table 12** for the study day and windows for clinical assessments.

Table 13: Patient Clinical Assessments/Testing																				
Patient Clinical Assessments/Testing	Baseline	Day pre or post-transplant																		
		-6 & -5	0	1	7	14	21	28	35	42	49	56	63	70	77	84	91	100	180	365
History, Physical Exam, Weight, and Height ¹	•		•		•	•	•	•	•	•	•	•	•	•	•	•	•	•	•	•
Karnofsky/Lansky Performance Status ¹	•																			•
Genetic testing ²	•																			
Diepoxybutane (DEB) or Mitomycin C (MMC) ³	•																			
Telomere testing by flow-FISH ⁴	•																			
PNH testing ⁵	•																			
HLA Typing ⁶ & Anti-Donor Antibody Testing ¹	•																			
CBC with differential and platelet count ^{1,7}	• ^{7e}	• ^{7d}	•		•	•	•	•	•	•	•	•	•	•	•	•	•	• ^{7c}	•	• ^{7e}
Blood chemistries ^{1,8} and liver function studies ^{1,9}	•	• ^{8d}	•		•	•	•	•	•	•	•	•	•	•	•	•	•	• ^{8c}	•	•
ABO/Rh ¹	•																			
PT/PTT/INR ¹	•																			
Serum ferritin & % iron saturation ¹	•																			•
Serum Immunoglobulins: IgG, IgM, and IgA ¹	•																•		•	•
Pregnancy test (females of childbearing potential) ¹	•																			
Infectious disease testing per institutional practice. Recommend CMV, HSV, VZV, toxoplasmosis, hepatitis B & C, HIV 1&2, HTLV 1&2, and syphilis ¹	•																			
CMV & EBV DNA Quantitative PCR Testing ¹⁰			•		•	•	•	•	•	•	•	•	•	•	•	•	•	• ^{10a} &	•	
Peripheral Blood Chimerism (Myeloid and CD3) ¹¹	•							•		•								•	•	•
Tacrolimus levels ¹²				•	•	•	•	•	•	•	•	•	•	•	•	•	•	• ^{12b}	•	
Lymphocyte subsets (absolute CD3, CD4, CD19, and CD56)																		•	•	•

Table 13: Patient Clinical Assessments/Testing																				
CXR or chest CT ¹³	•																			
		Day pre or post-transplant																		
Patient Clinical Assessments/Testing	Baseline	-6 & -5	0	1	7	14	21	28	35	42	49	56	63	70	77	84	91	100	180	365
EKG ¹ & Echocardiogram/MUGA ¹⁴	•																			
Pulmonary Function Tests ^{1,15}	•																			•
Assessment for hepatic or cardiac iron overload ¹⁶	•																			•
Bone marrow evaluation ¹⁷	•																			•
Acute +/- Chronic GVHD assessments ¹⁸					•	•	•	•	•	•	•	•	•	•	•	•	•	•	•	•
Toxicity assessments ¹⁹								•				•						•	•	•
Treosulfan PK Samples on peripheral blood ²⁰		•																		
Biology Studies ²¹	• ²¹																			• ²¹
Mutational Testing ²²	•																			
Health related quality of life (PROMIS) ²³	•																		•	•

1. Within 30 days prior to enrollment. In addition, for patients enrolled on the Treosulfan PK studies, the patient’s height and weight must be repeated if not already obtained within 3 days of the start of Treosulfan.

2. Genetic testing is required on all patients prior to enrollment (excluding patients with PNH). This testing does not need to be repeated pre-transplant if it has been previously done.

3. Diepoxybutane (DEB) or Mitomycin C (MMC) testing on peripheral blood or skin fibroblasts for Fanconi Anemia is required for all patients who lack a genetic mutation (excluding patients with PNH). This testing does not need to be repeated pre-transplant if it has been previously done.

4. Telomere testing by flow-FISH is required for all patients who lack a genetic mutation (excluding patients with PNH). This testing does not need to be repeated pre-transplant if it has been previously done.

5. PNH testing (for PNH patients only): Per institutional practice. Repeat PNH testing within 30 days prior to enrollment.

6. HLA typing may be completed at any time prior to enrollment.

7. CBC with differential and platelet count

- Day 0 until count recovery/engraftment (defined as an ANC > 0.5 x 10⁹/L x 3 consecutive measurements): Minimum three times per week.
- Count recovery/engraftment through day +100: Minimum weekly
- Day 101 through day +365: Minimum monthly
- For patients enrolled on the Treosulfan PK studies, a CBC is required in the morning on day -6 and -5 prior to the start of the Treosulfan infusion. This can be done in conjunction with standard of care tests.
- For patients enrolled in the Biological Studies, a CBC is required to be done on the same day as the sample collection. This can be done in conjunction with standard of care tests.

Table 13: Patient Clinical Assessments/Testing

8. Blood chemistries: sodium, potassium, chloride, bicarbonate, BUN, creatinine, calcium, magnesium, phosphorus
 - a. Day 0 through day +28: Minimum twice weekly.
 - b. Day +29 through day +100: Minimum weekly
 - c. Day +101 through day +365: Minimum monthly
 - d. For patients enrolled on the Treosulfan PK studies, a serum creatinine is required in the morning on day -6 and -5 prior to the start of the Treosulfan infusion. This can be done in conjunction with standard of care tests.
9. Liver function studies: Total and direct bilirubin, alkaline phosphatase, AST, and ALT
 - a. Day 0 through day +28: Minimum twice weekly
 - b. Day +29 through day +100: Minimum weekly
 - c. Day +101 through day +365: Minimum monthly
10. Peripheral blood CMV & EBV PCR monitoring
 - a. CMV PCR (peripheral blood): Day 0 through day +100 (minimum weekly or more often if clinical concerns) and then it is recommended to continue weekly or every other week monitoring of CMV PCR through day +180 due to receipt of serotherapy. Additional monitoring should be per institutional practice for patients with a history of CMV reactivation or CMV disease post-transplant or for those who remain on immune suppression.
 - b. EBV PCR (peripheral blood): Day 0 through day +100 (minimum weekly or more often if clinical concerns) and then it is recommended to continue weekly or every other week monitoring of EBV PCR through day +180 due to receipt of serotherapy. Additional monitoring should be per institutional practice for patients with a history of EBV reactivation or PTLTD post-transplant.
11. Peripheral blood chimerism studies (myeloid and CD3 T-cell)
 - a. Peripheral blood samples for chimerism analysis by molecular methods (patient and donor) at baseline (any time prior to study enrollment)
 - b. Day +28 (day +28 chimerism should only be evaluated if the patient has an ANC $\geq 0.5 \times 10^9/L$)
 - c. Day +42 (day +42 chimerism should only be evaluated if chimerism studies were not performed at day +28)
 - d. Day +100, +180, and +365
 - e. For patients with mixed chimerism, follow up chimerism studies per institutional practice is recommended to document sustained engraftment or graft failure
12. Tacrolimus levels:
 - a. Day +1 through day +28: Minimum twice weekly
 - b. Day +29 through day +100: Minimum weekly
 - c. Day +101 through day +180 or initiation of the tacrolimus taper whichever is later: minimum every other week then monthly per institutional practice
 - d. If there are concerns for renal dysfunction, the tacrolimus level should be followed more closely per institutional practice
13. CXR or Chest CT as clinically indicated or per institutional practice. It is recommended that patients with a history of neutropenia or underlying immunodeficiency have a CT scan of the chest, abdomen, and pelvis as well as the sinuses (if age appropriate) due to increased risk for infection including fungal disease
14. Echocardiogram/MUGA: Echocardiogram or MUGA for assessment of left ventricular ejection fraction (LV EF) or, for patients unable to obtain LV EF, LV shortening fraction (LVSF; within 3 months of study enrollment)
15. Pulmonary function testing (PFT): to include FEV1, FVC, FEV1/FVC, TLC, RV, and DLCO (corrected for hemoglobin). For patients who are unable to perform PFTs due to age or developmental delay, pulse oximetry is an acceptable alternative.
16. Assessment for hepatic or cardiac iron overload:

Table 13: Patient Clinical Assessments/Testing

- a. Formal assessment of hepatic and/or cardiac iron overload within 6 months of study enrollment using a validated methodology such as T2* MRI (liver and heart), ferriscan (liver), or biopsy (liver) per institutional practice.
 - i. For patients ≥ 18 years with a history of significant transfusions defined as ≥ 8 packed red blood cell transfusions per year for ≥ 1 year or have received ≥ 20 packed red blood cell transfusions (lifetime cumulative) will require formal hepatic and cardiac iron measurement. In addition, patients with a prior history of hepatic or cardiac iron overload will also require formal assessment for hepatic and cardiac iron overload.
 - ii. For patients < 18 years old with a history of significant transfusions defined as ≥ 8 packed red blood cell transfusions per year for ≥ 1 year or have received ≥ 20 packed red blood cell transfusions (lifetime cumulative) will require formal hepatic iron measurement. In addition, patients with a prior history of hepatic iron overload will also require formal assessment for hepatic iron overload.
 - b. Day +365: Follow-up assessment for hepatic and potentially cardiac iron overload is recommended for patients with a history of iron overload pre-HCT or those considered at risk for iron overload post-HCT per institutional practice.
17. Bone marrow aspirate and biopsy for pathology, flow cytometry, cytogenetics, and MDS FISH panel. The MDS FISH panel should evaluate for deletion 5q/monosomy 5, monosomy 7/deletion 7q, trisomy 8, and deletion 20q
 - a. Baseline (within 60 days prior to enrollment)
 - b. Day +365: Per the discretion of the treating physician a bone marrow evaluation around 1-year post-HCT.
 18. GVHD assessments: Patients should be assessed weekly until Day +100 post-HCT for GVHD. After Day +100, patients will be assessed at each follow-up visit through 12 months for the presence of GVHD.
 19. Toxicity assessments: At day +28, +56, +100, +180, and +365
 20. Treosulfan Pharmacokinetic Studies (Optional): Treosulfan pharmacokinetic sampling and analysis on peripheral blood samples on days -6 and -5. The same peripheral blood sample will be used for both Treosulfan and Treosulfan monoepoxide quantitation (samples will be split in PK Lab during analysis process). This will only be done in subjects/guardians who have provided consent. (see **Appendix E for additional details**)
 21. Biological Studies (Optional): Biological studies will be performed on peripheral blood and bone marrow (if a clinical marrow occurs) samples at baseline (within 60 days) and at Day +365 post-HCT, if consent is obtained from subjects/guardians (see **Appendix E for additional details**).
 22. Mutational Testing (Optional): Mutation studies will be performed in patients who lack a known genetic mutation responsible for their bone marrow failure phenotype at baseline, if consent is obtained from subjects/guardians (excluding patients with PNH; see **Appendix E for additional details**).
 23. Health related quality of life (Optional): Health related quality of life using the PROMIS instruments will be performed at baseline, day +180 and day +365 post-HCT in English and Spanish speaking patients only if consent is obtained from subjects/guardians.

